9.4.3.2 Severity

The severity of AEs and SAEs will be graded based on criteria from the Common Terminology Criteria for Adverse Events (CTCAE) Version 4.03, June 2010 (refer to [Appendix D](#)). Any AE not listed in [Appendix D](#) will be graded as follows:

- **Mild:** The event is easily tolerated by the subject and does not affect the subject's usual daily activities

- **Moderate:** The event causes the subject more discomfort and interrupts the subject's usual daily activities
- **Severe:** The event is incapacitating and causes considerable interference with the subject's usual daily activities

If the event is an SAE, then all applicable seriousness criteria must be indicated (criteria listed in [Section 9.3.3](#)).

9.4.3.3 *Action Taken with Study Drug*

Action taken with Study Drug (ISIS 678354 or placebo) due to the event is characterized by 1 of the following.

- **None:** No changes were made to Study Drug (ISIS 678354 or placebo) administration and dose
- **Temporarily Interrupted, Restarted – Same Dose:** Dosing was temporarily interrupted or delayed due to the AE and restarted at the same dose
- **Temporarily Interrupted, Restarted Reduced Dose:** Dosing was temporarily interrupted or delayed due to the AE and restarted at the next lower dose
- **Permanently Discontinued:** Study Drug was discontinued and not restarted

9.4.3.4 *Treatment Given for Adverse Event*

Any treatment (e.g., medications or procedures) given for an AE should be recorded on the Adverse Event Case Report Form. Treatment should also be recorded on the concomitant treatment or ancillary procedures eCRF, as appropriate.

9.4.3.5 *Outcome of the Adverse Event*

If the event is a non-serious AE, then the event's outcome is characterized by 1 of the following:

- **Ongoing:** Patient terminates from the trial and the AE continues
- **Recovered:** Patient recovered completely from the AE
- **Became Serious:** The event became serious (the date that the event became serious should be recorded as the Resolution Date of that AE and the Onset Date of the corresponding SAE)
- **Change in Severity (if applicable):** AE severity changed

If the event is an SAE, then the event's outcome is characterized by 1 of the following:

- **Ongoing:** SAE continuing
- **Persists (as non-serious AE):** Patient has not fully recovered but the event no longer meets serious criteria and should be captured as an AE on the non-serious eCRF (the SAE resolution date should be entered as the date of onset of that AE)

- **Recovered:** Patient recovered completely from the SAE (the date of recovery should be entered as the SAE resolution date)
- **Fatal:** Patient died (the date of death should be entered as the SAE resolution date)

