8.6.4 Stopping Rule for Bleeding

If an event of Major Bleeding or Clinically-Relevant Non-major Bleeding event occurs, the Investigator must notify the Sponsor Medical Monitor (or designee) and the subject should be closely monitored (vital signs, lab tests such as Hb, HCT and platelet count, additional outpatient visits, overnight stays and coagulation tests may be needed) throughout the treatment and during the post-treatment evaluation period.

In the event of Major Bleeding or Clinically-Relevant Non-major Bleeding (see definitions in [Section 8.5.4](#)) as assessed by the Investigator, dosing of a subject with Study Drug (ISIS 678354 or placebo) may be stopped permanently. The follow-up schedule for any events meeting this stopping criterion will be determined, including the suitability of the subject for resumption of dosing by the Investigator in consultation with the Sponsor Medical Monitor (or designee).

Table 3 Actions in Patients with Low Platelet Count

Platelet Count on Rx	Drug Dose	Monitoring
Normal range, $\geq 140K/mm^3$	No action	Monitor every 14 days (± 2 days)
$\geq 100K$ to $< 140K/mm^3$	No action	Closer observation Monitor every week*
$\geq 75K$ to $< 100K/mm^3$	Permanently reduce as follows: For Cohort A: reduce to 5 mg every 4 weeks For Cohort B: reduce to 25 mg every 4 weeks For Cohort C: reduce to 7.5 mg every 2 weeks For Cohort D: reduce to 5 mg every week	Closer observation Monitor every week*
$\geq 50K$ to $< 75K/mm^3$	Pause dosing When platelet count returns to $\geq 100K/mm^3$ restart dosing as follows only if approved by Sponsor Medical Monitor: For Cohort A: reduce to 5 mg every 4 weeks For Cohort B: reduce to 25 mg every 4 weeks For Cohort C: reduce to 7.5 mg every 2 weeks For Cohort D: reduce to 5 mg every week or Permanently discontinue Study Drug if it occurs while on already reduced dose	Closer observation Monitor every 2-3 days until 2 successive values show improvement Consider discontinuation of antiplatelet agents/non-steroidal anti-inflammatory drug (NSAIDS)

Platelet Count on Rx	Drug Dose	Monitoring
≥25K to <50K/mm ³	Permanently discontinue Study Drug	Closer observation: Monitor daily until 2 successive values show improvement then monitor every 2-3 days until platelet count stable Discontinue antiplatelet agents/NSAIDS while platelet count <50K/mm ³ if possible Refer to hematologist to provide diagnostic and therapeutic management

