9.4.3 Evaluation of Adverse Events (Serious and Non-Serious)

The Investigator's opinion of the following should be documented on the Adverse Event Case Report Form:

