An overview of AEs will be provided for all TEAEs. Treatment-emergent AEs, treatment-emergent SAEs, TEAEs related to Study Drug, treatment-emergent SAEs related to Study Drug, TEAEs that lead to Study Drug discontinuation, TEAEs that lead to Study Drug interruption, TEAEs that lead to dose reduction, and TEAEs leading to death will be listed. Note that imputed dates will be used for defining TEAEs and classification of TEAEs into analysis periods.

Listings of all AEs, TEAEs related to Study and Treatment Emergent SAEs related to Study will be presented. Originally reported dates will be used in listings.

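### The AE action-taken codes have no entry for a dose reduction without interruption, so the SAP listings of interruptions and reductions will misplace such events if they rest on that field alone

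*Combined protocol and SAP*

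**What the plan says.** Protocol Section 9.4.3 places the investigator's assessment of each AE on one form: it "should be documented on the Adverse Event Case Report Form". Section 9.4.3.3 then closes the list of actions: "Action taken with Study Drug (ISIS 678354 or placebo) due to the event is characterized by 1 of the following". The four definitions are:

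- None: "No changes were made to Study Drug (ISIS 678354 or placebo) administration and dose"
- Interrupted, same dose: "Dosing was temporarily interrupted or delayed due to the AE and restarted at the same dose"
- Interrupted, reduced dose: "Dosing was temporarily interrupted or delayed due to the AE and restarted at the next lower dose"
- Discontinued: "Study Drug was discontinued and not restarted"

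Protocol Table 3 sets the dosing action by platelet band. For 75,000 to below 100,000/mm³ the instruction opens "Permanently reduce as follows" and gives a lower dose for each cohort, with no pause. The next band down, 50,000 to below 75,000/mm³, does begin with a pause; a restart at the lower dose follows only on recovery and with approval. Section 8.7 also permits other adjustments for safety or tolerability, and names interrupting and decreasing the dose as separate options.

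SAP Section 3.7.2 promises listings that keep the two actions apart: "TEAEs that lead to Study Drug interruption, TEAEs that lead to dose reduction". It does not name the field or dataset that decides which AE goes in which list.

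**The concern.** The coding list treats a lower dose as something that happens only after a break in dosing. The protocol's own platelet rule has a step where the dose goes down and dosing continues. An investigator who follows that rule and then completes the AE form has no true answer to give. Choosing None denies a change that was made; choosing interrupted and reduced records a break that did not occur.

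What is at stake is attribution: which AEs led to a lower dose, and which led to a gap in dosing. The two SAP listings exist to show this. Other planned outputs do not replace them. Exposure and compliance (SAP Section 3.2.5) work on volumes and do not tie a reduction to an AE, and the stopping-rule tabulation in SAP Section 3.7.4 counts patients who stopped treatment.

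**Working it through.** The plan gives no figure on this point, so the check is a cross-mapping of the protocol's actions to its codes, and of the codes to the SAP's lists.

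**Step 1. Map each Table 3 band to the four codes.**

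| Platelets (/mm³) | Table 3 action | Code that fits |
|---|---|---|
| 140,000 or more | none | None |
| 100,000 to <140,000 | none | None |
| 75,000 to <100,000 | permanent reduction, no pause | no code |
| 50,000 to <75,000, restarted | pause, then lower dose | interrupted, reduced dose |
| 50,000 to <75,000, already on reduced dose | permanent stop | discontinued |
| below 50,000 (two rows) | permanent stop | discontinued |

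Only the 75,000 to <100,000 band has no matching code. A decrease under Section 8.7 without a break meets the same gap.

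**Step 2. Follow each possible code into the two SAP listings.** For an AE handled by reduction alone, the correct entries are: interruption list no, reduction list yes. Assume the lists are read from the action-taken field.

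| Code chosen | Interruption list | Reduction list | Result |
|---|---|---|---|
| None | no | no | missing from the reduction list |
| Interrupted, same dose | yes | no | both wrong |
| Interrupted, reduced dose | yes | yes | falsely in the interruption list |
| Discontinued | no | no | missing from the reduction list, and falsely in the discontinuation outputs |

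Codes giving the correct pair: 0 of 4. The two that a site would plausibly choose, None and interrupted with reduced dose, each leave exactly one list wrong.

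**Step 3. Check that the lists work elsewhere.** For the 50,000 to <75,000 band with a restart, the correct pair is yes/yes, and the interrupted, reduced dose code gives yes/yes. The fault is therefore specific to reduction without interruption.

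**Step 4. Limit the affected set.** An AE is affected only if all of these hold:

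- The low count is reported as an AE. Protocol Section 9.5.1 keeps laboratory findings judged not clinically significant out of AE reporting.
- No dose is delayed. The third code covers delay as well as interruption, and protocol Section 8.5 requires results meeting monitoring criteria to be retested before the next dose, ideally within 3 days. If that retest pushes a dose back, the third code fits.
- The listing is derived from the action-taken field alone.

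The second condition may bear differently on the regimens. A retest within 3 days should usually finish before a dose due 2 or 4 weeks later, and is more likely to collide with a weekly dose. This is an inference from the schedules; the documents do not state it.

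**The case against.** The strongest reply is that the documents do not show the listings must fail. SAP Section 3.7.2 names no source field. Dosing is recorded elsewhere: in a dosing diary entered into the eCRF (protocol Section 8.11) and on a dosing form (Section 9.5.3). The SAP is built on eCRF version 6.0, which is not among the documents and may carry a further option. All of this stands, so a reader who infers that the listings cannot be correct goes further than the text allows. It does not remove the point: the protocol's list as written has no true code, dosing records alone do not say which AE caused a change, and the SAP does not say that it uses them.

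A reader might also infer that the milder platelet events become invisible, or merge with the more serious ones, and that dose selection suffers. The documents do not support this. SAP Section 3.7.4 tabulates platelet nadirs in separate 75,000 to <100,000 and 50,000 to <75,000 rows, counts any single value below 100,000, and adds shift tables, all from laboratory data. Protocol Section 10.1.4 names the incidence of platelet reductions, which those tables serve; it does not name dose-modification rates.

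Finally, a reader might want a percentage, for example 1 to 3 of about 20 active patients per arm. That count would be an assumption with nothing in the documents behind it; protocol Section 2.3.4 reports no treatment-related platelet abnormalities in Phase 1. The SAP also defines no interruption or reduction rate to which it would apply. Its frequency tables by system organ class and preferred term cover permanent discontinuation and death, while interruption and reduction are only listed.

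**Conclusion.** The point holds in a narrow form. The four-code list in protocol Section 9.4.3.3 cannot record an action that Table 3 requires and Section 8.7 allows. If both SAP Section 3.7.2 listings are derived from that field alone, at least one is wrong for every AE handled by reduction without interruption or delay: absent from the reduction list if coded None, wrongly present in the interruption list if coded as interrupted and restarted at a reduced dose.

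The size is at least one wrong list placement per such AE; no rate can be given. The consequence is limited to attributing dose changes to AEs in descriptive safety output. Laboratory platelet summaries, the dose-selection criterion and every efficacy result stand as planned. The conclusion rests on two things that the documents leave open: that the eCRF mirrors the protocol's four codes, and that the listings use that field alone. This is a minor correction, worth making because it is cheap.

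**What to change.** Check the action-taken field in eCRF version 6.0. If it mirrors the protocol, add a fifth code, dose reduced and not interrupted, to protocol Section 9.4.3.3 and to the AE form. If the form already has such a code, align the protocol text with it.

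If the form is closed to change, add a sentence to SAP Section 3.7.2: both listings are derived from the dosing records (volume given and doses missed or delayed, against the cohort schedule), linked to the AE by date, and not from the action-taken field alone.

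The first route costs one category in the protocol and eCRF. The second costs a little programming to link dosing changes to AEs, using data already collected. Both change reporting only and leave the dosing rules as they are.

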9.5 Procedures for Handling Special Situations

9.5.1 *Abnormalities of Laboratory Tests*

Clinically-significant abnormal laboratory test results may, in the opinion of the Investigator, constitute or be associated with an AE. Examples of these include abnormal laboratory results that are associated with symptoms, or require treatment, e.g., bleeding due to thrombocytopenia, tetany due to hypocalcemia, or cardiac arrhythmias due to hyperkalemia. Whenever possible, the underlying diagnosis should be listed in preference to abnormal laboratory values as AEs. Clinically-significant abnormalities will be monitored by the Investigator until the parameter returns to its baseline value or until agreement is reached between the Investigator and Sponsor Medical Monitor that monitoring is no longer necessary. Laboratory abnormalities deemed not clinically-significant (NCS) by the Investigator should not be reported as AEs. Similarly, laboratory abnormalities reported as AEs by the Investigator should not be deemed NCS on the laboratory sheet.

The Investigator is responsible for reviewing and signing all laboratory reports. The clinical laboratory reports will serve as source documents and should include the Investigator's assessment of clinical significance of out of range/abnormal laboratory values and signatures.

All platelet count results must be reviewed promptly (within 48 hours of receipt) by the Investigator or the designee to ensure that the count has not met the stopping rule and to determine whether the rate of decline is suggestive that the patient could be approaching the dose interruption rule of 75,000/mm³ as specified in [Section 8.6.3](#).

Any case of a platelet count reduction to levels below 50,000/mm³ is considered an adverse event of special interest and should be reported in an expedited fashion to the Sponsor as per [Sections 9.3.3.1](#) and [9.4.1](#)).

All results of liver function tests must be reviewed promptly (within 48 hours of receipt) by the Investigator or the designee to ensure that the result has not met the stopping rules per [Section 8.6.1](#).

All results of renal function tests must be reviewed promptly (within 48 hours of receipt) by the Investigator or the designee to ensure that the result has not met the stopping rules per [Section 8.6.2](#).

Any event meeting renal stopping rules criteria described in [Section 8.6.2](#) is considered an adverse event of special interest and should be reported in an expedited fashion to the Sponsor as per [Sections 9.3.3.1](#) and [9.4.1](#)).

9.5.2 *Prescheduled or Elective Procedures or Routinely Scheduled Treatments*

A prescheduled or elective procedure or a routinely scheduled treatment will not be considered an SAE, even if the patient is hospitalized; the Study Center must document all of the following:

- The prescheduled or elective procedure or routinely scheduled treatment was scheduled (or was on a waiting list to be scheduled) prior to obtaining the patient's consent to participate in the study
- The condition that required the prescheduled or elective procedure or routinely scheduled treatment was present before and did not worsen or progress in the opinion of the Investigator between the patient's consent to participate in the study and the timing of the procedure or treatment. The condition is documented in the patient's medical history
- The prescheduled or elective procedure or routinely scheduled treatment is the sole reason for the intervention or hospital admission

9.5.3 *Dosing Errors*

Study Drug (ISIS 678354 or placebo) errors should be documented as Protocol Deviations. A brief description should be provided in the deviation, including whether the patient was symptomatic (list symptoms) or asymptomatic, and the event was accidental or intentional.

Dosing details should be captured on the Dosing Case Report Form. If the patient takes a dose of Study Drug (ISIS 678354 or placebo) that exceeds protocol specifications and the patient is symptomatic, then the symptom(s) should be documented as an AE and be reported per [Section 9.4](#).

Should an overdose occur, the Investigator or designee should contact the Sponsor or designee within 24 hours.

9.5.4 *Contraception and Pregnancy*

Male and female patients of childbearing potential must continue to use appropriate contraception with their partners, or refrain from sexual activity, as described in [Section 6.3.1](#).

If a patient becomes pregnant or a pregnancy is suspected, or if a male patient makes or believes that he has made someone pregnant during the study, then the Study Center staff must be informed immediately. An Initial Pregnancy Form should be submitted to the Sponsor or designee **within 24 hours** of first learning of the occurrence of pregnancy. Follow-up information including delivery or termination is reported by designating as 'Follow-up' on the Pregnancy Forms and reported within 24 hours of occurrence.

Payment for all aspects of obstetrical care, child or related care will be the patient's responsibility.

Female patients: If a suspected pregnancy occurs while on the study (including during the follow-up period), a pregnancy test will be performed. The patient with a confirmed pregnancy will be immediately withdrawn from treatment with Study Drug. However, the patient will be encouraged to complete the Post-treatment Follow-up portion of the study to the extent that study procedures do not interfere with the pregnancy. Regardless of continued study participation, the Investigator will assist the patient in getting obstetrical care and the progress of the pregnancy will be followed until the outcome of the pregnancy is known (i.e., delivery, elective termination, or spontaneous abortion). If the pregnancy results in the birth of a child, the Study Center and Sponsor may require access to the mother and infant's medical records for an additional 8 weeks

after birth. Follow-up will be performed to the extent permitted by the applicable regulations and privacy considerations.

Male patients: The progress of the pregnancy of a male patient's partner should be followed until the outcome of the pregnancy is known (i.e., delivery, elective termination, or spontaneous abortion). If the pregnancy results in the birth of a child, **the Study Center and Sponsor may request access to the mother and infant's medical records for an additional 8 weeks after birth.** Follow-up will be performed to the extent permitted by the applicable regulations and privacy considerations.

10. STATISTICAL CONSIDERATIONS

The sections below indicate the overall structure and approach to the analysis of this study. A detailed Statistical Analysis Plan (SAP) incorporating these sections below will be prepared separately. The SAP will outline all data handling conventions, including software, and specify additional statistical methods to be used for analysis.

The study objectives are listed in [Section 1](#).

10.1 Study Endpoints, Subsets, and Covariates

Efficacy and safety endpoints that will be evaluated after the last patient has completed the primary analysis time point are identified in the following sections.

The primary efficacy and safety analysis time point is at Week 25 for patients who received every 4-week dosing (Cohorts A and B) and at Week 27 for patients who received weekly or biweekly dosing (Cohorts C and D). For patients continuing treatment beyond the primary analysis time point additional supportive efficacy and safety analyses will be repeated at the completion of Study Drug treatment.

10.1.1 Primary Endpoint(s)

The primary efficacy analysis for the primary endpoint will be the pairwise comparison of percent change from Baseline to the primary analysis time point in fasting TG between ISIS 678354 treated groups and pooled placebo group in the FAS.

The data will be analyzed using an ANCOVA model with the baseline TG level as a covariate.

10.1.2 Secondary Endpoints

The secondary endpoints comprise the effect of ISIS 678354 as compared to placebo at the primary analysis time point on the following:

- Percent change from Baseline in apoC-III, TC, LDL-C, HDL-C, non-HDL-C, VLDL-C, apoB, and apoA-I
- Proportion of patients who achieve serum TG ≤ 150 mg/dL (≤ 1.7 mmol/L)
- Proportion of patients achieving TG ≤ 100 mg/dL (≤ 1.13 mmol/L)

10.1.3 Safety Endpoints

The safety analysis will be performed using the following parameters:

- AEs
- Vital signs and weight
- Physical examinations
- Clinical laboratory tests (serum chemistry, hematology, coagulation, urinalysis)
- Proportion of patients with platelet drop by severity, including platelet drop below lower limit of normal (LLN), platelet drop greater than 30% from Baseline, or any platelet drop meeting stopping rules.
- Proportion of patients with liver adverse events by severity, number of patients meeting liver stopping rules, and change in liver function tests by severity.
- Proportion of patients with renal adverse events by severity, number of patients meeting renal stopping rules, and change in renal function tests by severity.
- ECGs (including serial ECGs in a subgroup of patients undergoing serial PK sampling)
- Use of concomitant medications

10.1.4 Dose Selection

Dose selection for the further development will be based on the following efficacy and safety considerations; more than 1 dose may meet these criteria. An effective dose, or dose regimen, will be one that achieves a clinically-meaningful reduction in serum TG levels. Safety will be evaluated on the basis of incidence of expected and unexpected treatment-related SAEs, and other specific safety considerations including the incidence of platelet reductions.

